Project Description

The global COVID-19 pandemic has left a staggering level of morbidity, mortality, and societal and economic disruption in its wake (CDC, 2020). Initial publications indicated that sudden loss of smell and taste are cardinal, early, and potentially specific symptoms of COVID-19, in both symptomatic and otherwise asymptomatic individuals. While fever and cough are common symptoms of various viral infections, the potential specificity of chemosensory loss to COVID-19 may make it valuable in screening and diagnosis.

Our study published in September 2020 (Parma et al., 2020a) confirms and substantially extends previous reports showing that loss of smell and taste are associated with COVID-19. We found that the majority of our participants with COVID-19 reported a severe reduction in their sense of smell compared to before the onset of illness. Notably, this loss of smell was not associated with self-reported nasal obstruction, consistent with anecdotal reports. Furthermore, we found that qualitative changes in smell (odor distortions or phantoms) were relatively rare. We found that taste, and to a lesser extent, chemesthesia, were also significantly impaired in individuals with COVID-19. Taken together, these results suggest that COVID-19 profoundly affects chemosensory function across multiple sensory modalities, and that disruption of these may be a possible indicator of COVID-19.

Purpose:

With this planned study, I want to investigate persistent problems with smell, taste and chemesthesia (burning in the mouth) in patients who have undergone Covid-19 infection. There are a number of patients who contact the undersigned, at the Department of Oral Surgery and Oral Medicine, Faculty of Dentistry, UiO for treatment of disturbances in smell, taste and burning in the mouth after undergoing Covid-19 infection. This patient group is called Long Covid or Covid-long haulers. The purpose of the study is to investigate the following:

- 1) what kind of problems the subjects have with smell, taste and burning in the mouth
- 2) how long after undergoing Covid-19 infection do the subjects have these problems
- 3) How long does it take after Covid-19 before they get normal smell, taste and burning in the mouth

Individuals and methods:

Subjects with Long Covid will be recruited from the patient group who contact the Faculty of Dentistry, UiO for assessment and treatment. Subjects will undergo a thorough assessment of their sense of smell, taste and chemoesthesia function using an already validated questionnaire and established, internationally validated methods. The sense of smell will be checked using the Sniffin' sticks test, and taste function will be assessed using taste strips. No biological materials will be collected.

The smell test can tell whether subjects are at risk of complete loss of sense of smell (anosmia), reduced sense of smell (hyposmia) or distortion of smell (parosmia). The taste test tells whether subjects are at risk of complete loss of sense of taste (ageusia), reduced sense of taste (hypogeusia) or distortion of taste (dysgeusia).

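### Aim 3 asks for time to recovery, but the protocol recruits patients with persisting problems and describes one assessment with no follow-up

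*Protocol*

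**What the plan says.** The protocol's Purpose section sets the overall topic: "I want to investigate persistent problems with smell, taste and chemesthesia (burning in the mouth) in patients who have undergone Covid-19 infection". It then lists three aims without ranking them. The first is the kind of problem. The second is "how long after undergoing Covid-19 infection do the subjects have these problems". The third is "How long does it take after Covid-19 before they get normal smell, taste and burning in the mouth".

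The Individuals and methods section gives the sampling: "Subjects with Long Covid will be recruited from the patient group who contact the Faculty of Dentistry, UiO for assessment and treatment". It gives the data collection as: "Subjects will undergo a thorough assessment of their sense of smell, taste and chemoesthesia function using an already validated questionnaire", together with established test methods. The named tests are these: "The sense of smell will be checked using the Sniffin' sticks test, and taste function will be assessed using taste strips". No test is named for burning.

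Neither section mentions a second assessment, a length of follow-up, a criterion for normal function or a recovered comparison group.

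**The concern.** Aim 3 is a time-to-event question. It needs an origin (the infection), an event (return to normal) and observation that continues long enough for the event to occur. The methods supply none of the third element. They also enrol patients at a point chosen because recovery has not yet happened, at least for the problem that made them seek help.

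The one duration that such a visit yields directly is time since infection. That is the time from infection to seeking care among people who are still affected. If it were reported under aim 3, readers and patients would take a time to presentation for a time to recovery. Patients who present while still affected also over-represent slow recoverers, so even a correctly measured duration would not describe Covid-19 patients in general.

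**Working it through.** The protocol gives no sample size, event count or follow-up length, so there is no figure of its own to reproduce. The check is whether the described data can identify the quantity in aim 3.

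**Step 1: likelihood at a single visit.** Let T be the time from infection to recovery of one modality, with survivor function S(t) = P(T > t). Take a patient who enters at time a because that modality is still affected, and who is observed only at a.

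- Probability of being still affected at a: S(a).
- Probability of entering, given entry at a while affected: S(a).
- Conditional contribution: S(a)/S(a) = 1, whatever S is.

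For that modality the contribution carries no information on S. With only such contributions, a Kaplan-Meier curve stays at 1.0 and no median can be estimated. The result requires three conditions: the modality is still abnormal at a, observation ends at a, and the analysis conditions on entry time.

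**Step 2: can elapsed time at the visit substitute?** The following values are assumptions for illustration; none comes from the protocol. Recovery is exponential with rate h = ln2/M, where M is the true median in months. Contact with the clinic is exponential with rate c. A person is sampled only if contact precedes recovery. Elapsed time at contact among those sampled is then exponential with rate h + c, so its median is ln2/(h + c). Set h + c = ln2/4 = 0.1733 per month.

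| True median M (months) | h | c = 0.1733 − h | Median elapsed time at visit (months) | Median total duration among those sampled (months) |
|---|---|---|---|---|
| 6 | 0.1155 | 0.0578 | 4.0 | about 12 |
| 12 | 0.0578 | 0.1155 | 4.0 | about 18 |
| 24 | 0.0289 | 0.1444 | 4.0 | about 30 |

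The last column follows because total duration is the sum of two independent exponentials, with rates k = h + c (time to contact) and h (remaining time). Its survivor function is [k·exp(−ht) − h·exp(−kt)]/(k − h). For M = 6 and t = 12 this is (0.1733 × 0.25 − 0.1155 × 0.125)/0.0578 = 0.50.

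The common 4.0 months is built into the chosen rates. That is the purpose of the example: without knowledge of the care-seeking rate, very different recovery times can give the same data at one visit. It does not estimate anything about this study. The last column shows the over-representation of slow recoverers.

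**Step 3: what follow-up would add.** A patient who enters at a, is still affected at a later contact l and has recovered by the next contact r contributes [S(l) − S(r)]/S(a). One still affected at the end of follow-up e contributes S(e)/S(a). Both depend on S, so aim 3 becomes estimable from entry onwards.

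**The case against.** A reader might infer that the study is cross-sectional by design. The protocol does not say so. One visit is inferred from the singular wording and from the absence of any follow-up. The patients come for treatment as well as assessment, so later contact is plausible. This stands, but it does not rescue aim 3: if follow-up is intended, its timing and length have to be written down. A statistical analysis plan that is not shown could not supply them, because whether patients are assessed again is protocol content and no analysis can create unobserved recoveries.

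A reader might also infer that the study holds zero information on aim 3 at any sample size, with every subject censored. That goes too far. Step 1 applies to a modality still abnormal at the visit. Aim 3 covers smell, taste and burning, and a patient who presents with one may already have recovered another. The questionnaire's content is not shown and might record when that happened. Entry depends on contacting the clinic, not on an abnormal test, so a normal smell or taste result at the visit is possible. A current-duration analysis of elapsed times is possible in principle, but it needs steady incidence and care-seeking unrelated to time since infection. The protocol supports neither for self-referred patients in a pandemic. What remains is weak, recall-based or assumption-dependent information, which is not nothing but is no sound basis for aim 3.

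Finally, the protocol shows no reporting plan for aim 3, so it cannot be said that a wrong figure will be published. The point is that the described data offer no sound figure to publish.

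**Conclusion.** The concern holds in this form: aim 3 needs recovery to be observed, and the protocol specifies no follow-up in which to observe it. For the presenting problem, recovery time is right-censored at entry if the study runs as written. The size cannot be put as a bias in months, because the protocol gives no durations and the table above rests on assumed rates.

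The conclusion assumes that the one assessment described is the whole of the data collection and that the presenting problem is still there at that assessment. One of three stated aims is affected. The kind of problem (aim 1) and elapsed time at presentation (a workable reading of aim 2) can be described from a single visit. The gap should be closed before anything is reported under aim 3.

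**What to change.** Choose one of two changes.

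- **Keep aim 3 and specify follow-up.** Contact all subjects at fixed times that do not depend on their returning for care, for example by sending the same questionnaire remotely. Repeating measurements only when patients come back would tie observation to persisting symptoms and miss those who recover. State the interval and total length, a definition of recovery for each modality (burning included, for which no test is named), and the infection date as time origin. Use an analysis that allows for delayed entry at enrolment and for interval and right censoring. Limit conclusions to care-seeking Long Covid patients.
- **Delete or reword aim 3.** State that the study describes the type of problems and the time since infection at presentation only.

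The first option costs a protocol amendment, added questionnaire work and some non-response; the protocol gives no sample size or staffing from which to cost it. The second needs almost no work but narrows the claim. Under either option, state that time since infection at the visit will not be presented as time to recovery.

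### Aims 2 and 3 count time from infection, but subjects enter only on contacting the clinic with a problem still present, so early recoverers are left-truncated and visit time is only a censored lower bound on duration

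*Protocol*

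**What the plan says.** **Who is studied.** The Purpose section states: "I want to investigate persistent problems with smell, taste and chemesthesia (burning in the mouth) in patients who have undergone Covid-19 infection". It describes people who approach the department "for treatment of disturbances in smell, taste and burning in the mouth after undergoing Covid-19 infection" and adds: "This patient group is called Long Covid or Covid-long haulers". Individuals and methods then gives the only recruitment rule: "Subjects with Long Covid will be recruited from the patient group who contact the Faculty of Dentistry, UiO for assessment and treatment".

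**What is asked about time.** Aim 2 is "how long after undergoing Covid-19 infection do the subjects have these problems". Aim 3 is "How long does it take after Covid-19 before they get normal smell, taste and burning in the mouth".

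**What is measured.** "Subjects will undergo a thorough assessment of their sense of smell, taste and chemoesthesia function using an already validated questionnaire", and "The sense of smell will be checked using the Sniffin' sticks test, and taste function will be assessed using taste strips". One assessment is described. The protocol mentions no later visit, follow-up period, definition of recovery or date of recovery.

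**The concern.** The clock in aims 2 and 3 starts at infection, but observation starts at clinic contact, and contact requires that the problem has not yet resolved. Two separate difficulties follow.

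- **Left truncation.** People whose smell, taste or burning returned to normal before they made contact are absent. Any duration or recovery curve drawn from infection in this sample treats the months before contact as time in which a subject could have recovered and been counted. No entrant could have done so.
- **Censoring at the visit.** For a subject still affected at the assessment, time since infection shows only that the problem has lasted at least that long. Its value depends partly on when the person chose to make contact.

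The answers to two of the three aims are at stake. An analysis plan can name a method, but it cannot supply later observations or people who never entered.

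**Working it through.** **Reproduction.** The protocol states no sample size, follow-up length or duration, so there is no figure to reproduce. What follows shows direction and possible size under assumed values only.

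**Notation.** T is the time from infection to recovery, with density f and survival function S. A is the time from infection to clinic contact. A subject enters only if T > A; this condition comes from the Purpose section and Individuals and methods. T and A are assumed independent.

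**Step 1: total duration among entrants.** Assume A is uniform on 0 to 24 months. The density of T among entrants is then proportional to f(t) × min(t, 24). Solving for the median by numerical integration:

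| Assumed distribution of T | True median | Median among entrants | Ratio |
|---|---|---|---|
| Exponential | 2 months | 4.84 | 2.42 |
| Log-normal, log-SD 1 | 2 months | 5.29 | 2.65 |
| Exponential | 6 months | 13.68 | 2.28 |
| Log-normal, log-SD 1 | 6 months | 13.52 | 2.25 |

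If instead everyone makes contact at exactly 3 months and T is exponential, the median among entrants is 3 + true median, because the exponential has no memory. True medians of 1, 2 and 6 months appear as 4, 5 and 9.

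**Step 2: sensitivity.** Simulation used a true median of about 2 months (exponential with mean 3, or log-normal with log-SD 1 or 1.5). Contact was fixed at 3 months, uniform on 1 to 12, or uniform on 0 to 60. The median among entrants ranged from 5 to 15.5 months. The top value comes from the heaviest tail with the widest contact window. The direction is the same throughout, but the size is not pinned down.

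**Step 3: time since infection at the visit.** In the Step 1 scenario the density of A among entrants is proportional to S(a) on 0 to 24. For the exponential with rate λ = ln 2 / true median, the median is −ln[1 − 0.5(1 − e^(−24λ))] / λ.

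- True median 2: e^(−24λ) = 2^(−12) = 0.00024, giving 2.00 months.
- True median 6: e^(−24λ) = 2^(−4) = 0.0625, giving −ln(0.53125) / 0.1155 = 5.48 months.
- Log-normal, log-SD 1, by numerical integration: 2.19 and 5.31 months.

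Visit time therefore lands near the true median here, a little above for 2 months and below for 6. That is an accident of the assumed contact pattern: with contact fixed at 3 months it would be 3 whatever the true duration. In the Step 2 scenarios it averaged 45% to 60% of the subject's own full duration.

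**Step 4: what delayed entry does when there is follow-up.** Assume log-normal T with median 2 months and log-SD 1, contact uniform on 1 to 12 months, and 12 months of follow-up after the visit. The true proportion still affected, among those lasting beyond 1 month, is Φ(−ln(t/2)) / Φ(ln 2). At 3 months this is 0.343 / 0.756 = 0.45.

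| Months since infection | True | Kaplan-Meier, late entry ignored | Kaplan-Meier, entry at visit |
|---|---|---|---|
| 3 | 0.45 | 0.84 | 0.44 |
| 6 | 0.18 | 0.53 | 0.17 |
| 12 | 0.05 | 0.19 | 0.05 |

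Delayed entry recovers the curve, given survival to the earliest entry time and contact time independent of duration. It works only because subjects are observed after the visit. If the visit is both entry and exit, there is no time at risk.

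**The case against.** The best reply is that target and sample already match. The Purpose section speaks of persistent problems, gives the care-seeking group the Long Covid label, and frames aims 1 and 2 around the subjects themselves. On that reading people who recovered early lie outside the question, and leaving them out is not a bias. Much of this stands: a description confined to this clinic's patients is legitimate, and the protocol makes no duration or prevalence claim for everyone infected. It does not dispose of the point, because aim 3 asks for recovery time after Covid-19. Even for the enrolled group, duration is censored at the visit, and a curve drawn from infection without late entry is wrong.

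A reader might infer four stronger things that the document does not support.

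- **That time since infection at the visit is inflated.** Step 3 shows it need not be. The protocol also never says this time will serve as the duration; aim 2 can be read as time since infection at presentation.
- **That the sample is length-biased.** Sampling proportional to duration needs steady incidence, which the protocol does not claim. Left truncation is the accurate description.
- **That the clinic's case mix invalidates aim 1.** Aim 1 asks only what problems the subjects have. Taking the answer as the general Covid-19 pattern would be a reader's error, not one in the plan.
- **That every non-persistent case was meant to be covered.** The Purpose section's reference to persistent problems points the other way.

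It may also be said that delayed entry is a matter for the analysis plan. The method is. Whether anyone is observed after enrolment is a matter of design.

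**Conclusion.** The point holds in a limited form. Entry conditional on a continuing problem, combined with a clock that starts at infection, means that total duration or recovery time from this sample overstates the course among all affected patients. The size is unknown. With contact uniform over 0 to 24 months the median is about 2.25 to 2.65 times too long, and heavier tails or wider contact windows give larger factors. These factors rest on assumed distributions and on contact being independent of duration. They apply to total duration compared with all affected patients, and must not be applied to time since infection at the visit, which is a censored lower bound whose average over subjects may fall above or below the true duration. With only the assessment described, aim 3 yields no observed recovery time for a subject still affected at that visit.

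**What to change.** 1. State in the Purpose section that the aims apply to patients seeking care at this clinic with persistent chemosensory problems after Covid-19.
2. Reword aim 2 as time since infection at presentation.
3. Record four dates for each subject: infection, symptom onset, first contact and assessment.
4. Keep aim 3 only if recovery, suitably defined, is observed after enrolment. Subjects then join the risk set at enrolment and are censored if not recovered when last seen. Otherwise drop aim 3's recovery-time claim.
5. Make no duration claim for Covid-19 patients in general.

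**Cost.** Items 1, 2, 3 and 5 need only wording and four fields on the case form. Item 4 needs contact with subjects after enrolment if aim 3 is kept; the analysis itself is standard. The conclusion becomes narrower, and intervals at early times become wider because few subjects are at risk then. Dates not collected at the time may be hard to recover later, so the change is best made before enrolment proceeds.
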